## 12.2. Clinical Laboratory Evaluations

Laboratory data will be graded according to NCI CTCAE version 3.0. Shift tables demonstrating the changes from baseline to the worst severity grade observed during the treatment phase will be displayed for each treatment arm for relevant lab parameters for hematology, chemistry, and urinalysis.

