Analysis and Reporting

In addition to the interim analyses focusing on toxicities and disease progression, efficacy analyses will be performed when 80% of the subjects have progressed or died, or five years after the last subject was randomized, whichever occurs later.

Figure 1: Overall Study Schema

[figure not shown]

Table 2: Schedule of Assessments

Procedure ^a	Screen- ing ≤28 days prior to Day	Study Day 1	Days 2 and 4 for Cycle 1 and the first cycle at Dose Level +1,+2,+3,+4 +/- 1 day	Days 8, 15, 22 of Cycle 1 and first cycle at Dose Level +1, +2,+3, +4 Days 8 and 15 of Cycle 2 +/- 2 days	Every 28 days (4 wks) ^{b, c} (1 st day of each cycle)	At time of clinical manifestation of TFR	At time of clinical resolution of TFR	CR/CRi/ PR confirma- tion visit	Treat- ment discon- tinuation ^c	Every 12 weeks (+/- 7 days) until study closure
ICF/Inclusion/Exclusion	X					- 1				
Clinical staging for CLL (Rai or Binet classification)	X					+				
Medical history	X				2	2-				
Pregnancy test ^d	X ^d	X^d			X ^d				X ^d	
Pregnancy and risk counseling	Xe	Xe			Xe				X ^e	
ECOG Performance Status	X	X			X				X	
Evaluation of constitutional symptoms	X	X			X		-		X	
Physical examination to assess lymph nodes, spleen and liver	X	X	(\	X				X	
Vital signs including weight, height (at screening only) ^g	X	X	Х	X	X				X	
CT scans ^h	X	-	V -					X^h	X^h	
ECG (12 lead) ⁱ	X				X (starting at C3D1 then every 84 days thereafter)				Х	
TLS monitoring and prophylaxis and TFR monitoring	x	X	X	X	X					

Table 2: Schedule of Assessments (Continued)

Procedure ^a	Screen- ing ≤28 days prior to Day	Study Day 1	Days 2 and 4 for Cycle 1 and the first cycle at Dose Level +1,+2,+3,+4 +/- 1 day	Days 8, 15, 22 of Cycle 1 and first cycle at Dose Level +1, +2,+3, +4 Days 8 and 15 of Cycle 2 +/- 2 days	Every 28 days (4 wks) ^{b, c} (1 st day of each cycle)	At time of clinical manifestation of TFR	At time of clinical resolution of TFR	CR/CRi/ PR confirma- tion visit	Treat- ment discon- tinuation ^c	Every 12 weeks (+/- 7 days) until study closure
Hematology ^k	X	X	X	X	X	7/-	-		X	
Chemistry ^l	X	X	X	X	X	-	1	-	X	
Urinalysis ^m	X	X	X	X	X	7			X	
Calculated (method of Cockroft-Gault) creatinine clearance (24-hour collection method may also be used at the investigator's discretion) ¹	X		-		ZP.	-	1		1	
Direct antiglobulin (DAT) test ⁿ	X			<	-					
Thyroid function test ^o	X			QP.	X (starting at C3D1 then every 84 thereafter)				X	

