- j. TLS prophylaxis, comprising of oral hydration and allopurinol 300 mg/day will be initiated at least 3 days prior to starting study drug and for a minimum of the first 3 treatment cycles. For subjects with known allergy to allopurinol prior to study initiation or for those who develop an allergy during the course of study therapy, the medical monitor should be contacted. To maintain fluid intake, subjects should be instructed to drink 8-10 eight ounce glasses of water each day for the first 14 days of each cycle during the dose escalation period. Hydration levels should be adjusted according to age and clinical status, and lowered if the subject's cardiovascular status indicates the possibility of volume overload.
- k. Hematology: Local lab assessments include HGB, ANC, ALC and platelet count. At screening, subject must meet eligibility criteria based on central lab results. At Study Day 1, subject must meet eligibility criteria based on local or central lab results prior to initiating study therapy
- 1. Chemistry: Local lab assessments include potassium, calcium, phosphorus, creatinine, total bilirubin, AST/SGOT, ALT/SGPT, and uric acid. At screening, subject must meet eligibility criteria based on central lab results. At Study Day 1, subject must meet eligibility criteria based on local or central lab results prior to initiating study therapy, however, a re-calculation of creatinine clearance is not required at Study Day 1.
- m. Urinalysis: Local laboratory assessments will include ketones, sediments and specific gravity.
- n. DAT (direct antiglobulin test) will be performed at screening and analyzed at the central laboratory. The DAT test should be repeated if the investigator suspects hemolytic anemia during the course of the study. Analysis of DAT will be completed by local laboratory as part of this amendment, protocol amendment #6.
- o. TSH (thyroid-stimulating hormone), free T3, and free T4 levels will be assessed at screening, Cycle 3 Day 1 and every 12 weeks while on study drug and at treatment discontinuation. All samples will be analyzed centrally. Collection of TSH samples is discontinued as of this amendment, protocol amendment #6.

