response/relapse < 6 mo), 42% had prior FCR or PCR and 21% had prior alemtuzumab. The TLS prevention strategy resulted in only 2 (3.8%) cases of TLS, both observed at 2.5 mg/daily (1 patient with Grade 2 and another with lab TLS). Grade 3/4 tumor flare occurred in 5 (9.6%) patients and was managed with NSAIDs or low-dose steroids. The most common Grade 3/4 adverse events (AEs) included neutropenia (65%) and thrombocytopenia (33%). Febrile neutropenia occurred in 4 (8%) patients. Grade 3/4 infections were observed in 21 (40%) patients; 10 (19%) patients developed pneumonia and 3 developed sepsis; 2 cases of sepsisrelated death at day 37 and 94 of therapy were also noted but deemed unrelated to study drug by the investigators. Reasons for study discontinuation included disease progression (37%), AE's (29%), consent withdrawal (15%), death (4%), other reasons (10%). For 16 (31%) patients, 2.5 mg/daily was the maximum dose reached and 22 (42%) patients were unable to escalate beyond 5 mg/daily. Grade 4 neutropenia was the primary reason for delay in dose escalation. By intentto-treat (ITT) analysis, 6 patients (12%) had a partial response (NCI-WG 1996), 30 patients (58%) had stable disease and 13 patients (25%) progressed; 3 patients were non-evaluable. Median duration of treatment was 3.1 months (range, 0.07-18.4) and the median time to response was 4.3 months (range, 2.8-7.4). Responses were observed at 10 mg/daily (n=3), at 15 mg/daily (n=1), and at 20 mg/daily (n=2); Median PFS (ITT) was 5.5 months and median PFS for responders was 12 months. Three patients still remain on therapy and were transferred to commercial lenalidomide. (Data on file at Celgene)

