### 12.1. Adverse Events

The adverse events of Neutropenia, Anemia and Thrombocytopenia will be analyzed according to the grading system as recommended by the IWCLL guidelines for the diagnosis and treatment of CLL (Hallek, 2008).

The adverse event of Tumor Lysis Syndrome (TLS) will be analyzed according to the grading system as recommended by Cairo-Bishop grading system.

Treatment emergent adverse events (AEs) will be summarized by treatment arm and overall. A treatment emergent adverse event is defined as any AE occurring or worsening on or after the first treatment of any study drug, and within 30 days after the last dose of the last study drug received. Adverse events will be presented in descending order of frequency (for all subjects) by SOC, and then within each SOC, by decreasing order of preferred term. Adverse events are documented on the CRF together with their severity, according to the NCI CTCAE version 3.0 or higher, also referred to as NCI toxicity grading. For the categorization of the adverse events, the MedDRA® dictionary (version 15.0) will be used.

AE frequency will be tabulated by body system, MedDRA preferred term for each treatment regimen during the Treatment Phase as well as for the Follow-up Phase when appropriate. In the by-subject analysis, a subject having the same event more than once will be counted only once and by the greatest severity. AEs will be summarized by worst NCI CTCAE version 3.0 grade. In the case that the AEs or event frequencies are judged to be clinically important, an exact test may be used to analyze the difference between the treatment arms. Events of interest will also be summarized by treatment cycles.

AEs leading to death or to discontinuation from treatment, events classified as NCI CTCAE version 3.0 Grade 3, 4, and 4 AEs, treatment-related events, serious adverse events (SAEs) and events of interest (including second primary malignancies) will be summarized separately.

Individual AE listings by subject will be provided.

As an exploratory analysis, AEs will be summarized by treatment arm and by subgroup (i.e., relapse vs. refractory, age <65 vs. age ≥65, lines of prior CLL treatment, gender).

Adverse events (AE) will be classified using the Medical Dictionary for Regulatory Activities (MedDRA) classification system. The severity of the toxicities will be graded according to the NCI CTCAE version 3.0 whenever possible.

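### Blood counts are scheduled more often in subjects who escalate, so whole-treatment worst-grade tables by arm are open to detection bias of uncertain direction; add tables on a common schedule

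*SAP*

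**What the plan says.** Protocol Table 2 marks hematology and chemistry in the column headed "Days 2 and 4 for Cycle 1 and the first cycle at Dose Level +1,+2,+3,+4", in the column headed "Days 8, 15, 22 of Cycle 1 and first cycle at Dose Level +1, +2,+3, +4 Days 8 and 15 of Cycle 2", and at the 28-day visits. Its footnote on hematology reads "Hematology: Local lab assessments include HGB, ANC, ALC and platelet count". The tumor lysis monitoring text (Synopsis and Section 10.4.1.1) gives the same pattern but ties the dense visits to each dose escalation.

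Sections 8.1.6 and 10.2.2 make escalation depend on individual tolerability. They give Arm 1 four steps to 25 mg, Arm 2 three and Arm 3 two.

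SAP 12.2 states: "Shift tables demonstrating the changes from baseline to the worst severity grade observed during the treatment phase will be displayed for each treatment arm". SAP 12.1 states: "AEs will be summarized by worst NCI CTCAE version 3.0 grade", and allows an exact test between arms for events judged clinically important. SAP 6.5.1 adds worst-case summaries over the whole study, uses no visit windows, and provides for by-cycle presentation where applicable. The visible SAP text restricts no table to common time points and does not report how many draws each subject had.

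**The concern.** The worst of many measurements tends to be more severe than the worst of few. Here the number of measurements is set after randomization by tolerability, which is what the tables are meant to compare. Safety by starting dose is the primary objective, and cytopenias are the main severe toxicity in the protocol's background data: Grade 3/4 neutropenia was 65% in the sponsor's CLL-001 study and 70% in the single-agent study that started at 25 mg (Section 5.3.2). If the arms differ in how often subjects escalate, part of any difference, or lack of one, could come from how often counts were taken.

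There is also a route that does not depend on tolerability. If dense visits follow each actual escalation, Arm 3 has two dense escalation cycles and Arm 1 has four.

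**Working it through.** The documents state no figure for this point, so there is none to reproduce.

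**1. Scheduled draws, Cycles 1-5 (Table 2).** Dense cycle: Days 1, 2, 4, 8, 15, 22 = 6. Cycle 2 without escalation: Days 1, 8, 15 = 3. Later cycle without escalation: Day 1 = 1. Escalations are taken in consecutive cycles from Cycle 2.

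| Escalations | Draws per cycle | Total |
|---|---|---|
| 0 | 6+3+1+1+1 | 12 |
| 1 | 6+6+1+1+1 | 15 |
| 2 | 6+6+6+1+1 | 20 |
| 3 | 6+6+6+6+1 | 25 |
| 4 | 6+6+6+6+6 | 30 |

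Read by actual escalations, fully tolerant subjects in Arms 1, 2 and 3 have 30, 25 and 20 draws. Read by the dose-level labels +1 to +4 of Table 4, which repeats 25 mg at the upper levels, all three have 30. The documents leave this open.

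**2. Chance that a scheduled draw catches an episode.** Assume onset is uniform over a 28-day cycle and the episode lasts L days. Then P = Σ min(gap, L)/28 over the gaps between draws. The gaps are 1, 2, 4, 7, 7, 7 (dense); 7, 7, 14 (Cycle 2 without escalation); 28 (Day 1 only).

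| L | Dense | Cycle 2, no escalation | Day 1 only |
|---|---|---|---|
| 3 days | 15/28 = 0.54 | 9/28 = 0.32 | 3/28 = 0.11 |
| 7 days | 1.00 | 21/28 = 0.75 | 7/28 = 0.25 |
| 14 days | 1.00 | 1.00 | 14/28 = 0.50 |

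**3. Effect on the per-subject worst grade.** Assumptions not in the documents: true risk 30% per cycle in both arms, 7-day episodes, 30% against 60% never escalating, the rest escalating every cycle, and no non-escalator already recorded at Grade 4.

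- Five cycles, full escalator: 1 - 0.70^5 = 0.832. Never-escalator: 1 - 0.70 × 0.775 × 0.925^3 = 0.571.
- By arm: 0.7 × 0.832 + 0.3 × 0.571 = 0.754, against 0.4 × 0.832 + 0.6 × 0.571 = 0.675. That is about 75% against 68%, or 2.7 of 35 subjects.
- Three cycles: 1 - 0.70^3 = 0.657 and 1 - 0.70 × 0.775 × 0.925 = 0.498. By arm 0.609 against 0.562, about 61% against 56%, or 1.7 of 35 subjects.

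**4. Does the direction hold?** Change the assumptions to 20% risk per cycle and 80% against 40% escalating, and let a share c of non-escalators already carry a recorded Grade 4. The gap is the arm that escalates less minus the other arm, over five cycles.

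| L | c | True gap (points) | Recorded gap (points) |
|---|---|---|---|
| 7 days | 0 | 0 | -10.2 |
| 7 days | 0.5 | 6.6 | 1.4 |
| 7 days | 1 | 13.1 | 13.1 |
| 3 days | 1 | 13.1 | 22.7 |

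The bias can create a false difference, shrink a true one, vanish, or exaggerate a true one.

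**5. After restriction to common time points.** Every subject treated through Cycle 5 has 6+3+1+1+1 = 12 scheduled draws in every arm, so the schedule no longer differs between arms.

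**The case against.** The strongest reply is in the protocol's own account of CLL-001: "Grade 4 neutropenia was the primary reason for delay in dose escalation". A subject held back for that reason already has the worst neutrophil grade on record, and fewer later draws cannot lower it. Protocol Table 5 then requires weekly counts during the interruption. This stands, and it defeats any claim that neutropenia must be understated in the least tolerant subjects.

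It does not dispose of the point. Table 5 triggers weekly counts only at ANC below 500/µL, at ANC below 1,000/µL with fever, or at platelets below 20,000/µL. Grade 3 neutropenia without fever and anemia have no such trigger. Nor does it cover a second cell line, most chemistry shifts, subjects held back for other or milder events, or cycles after drug is resumed.

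Three further replies have weight:
- Adverse events are not captured only at scheduled draws. Appendix 21.1 counts any laboratory abnormality that needs treatment or a dose change.
- The trial compares whole escalation strategies (SAP 6.3), so a Cycle 1 table answers a narrower question and should not displace the whole-treatment table.
- After a delay, Day 1 of the next cycle is the day treatment resumes (Section 10.2.3). After Grade 4 neutropenia that day falls after recovery by rule, so a comparison on cycle Day 1 alone could hide events.

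The by-cycle provisions in SAP 6.5.1 and 12.1 help, but they do not equalize the draws within a cycle.

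**Conclusion.** The schedule imbalance is confirmed from the documents, and the visible SAP text does not address it. Whole-treatment worst-grade tables by arm are open to detection bias that may shrink or distort differences between starting doses. Exposure is mainly to Grade 3 neutropenia, anemia, a second cell line, chemistry shifts, and subjects held back for other or milder events.

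A reader might infer that the tables necessarily understate cytopenias where tolerability is worst. The documents do not support that: step 4 shows the sign depends on how many non-escalators already have Grade 4 recorded and on episode length, and neither is given. A reader might also take the 42% in CLL-001 who could not go beyond 5 mg as a never-escalation rate. That study started at 2.5 mg, so reaching 5 mg was itself an escalation.

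The illustrated size is about 5 to 8 percentage points per subject over three to five cycles, and it rests wholly on assumed risk, episode length and escalation rates. The shorter horizon matters because median treatment in CLL-001 was 3.1 months. How toxicity drives the interim decisions to drop an arm cannot be judged, because those rules are redacted. This is an inexpensive safeguard for the primary safety comparison, not a flaw that invalidates it.

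**What to change.** Keep the whole-treatment worst-grade tables as planned. Add to SAP 12.1 and 12.2:

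- (a) a worst-grade table for Cycle 1, where all arms share the same scheduled draws and the starting doses differ by design;
- (b) a sensitivity shift table limited to time points scheduled for every treated subject: all Cycle 1 draws, Cycle 2 Days 1, 8 and 15, then the 28-day assessments. For the last, use the visit that Table 2 footnote b requires every 28 days, not a delayed cycle Day 1 that follows recovery;
- (c) the number of hematology draws per subject by arm, printed beside the whole-treatment table.

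Also state whether dense visits followed the nominal dose-level labels or each actual escalation, since Table 2 and the monitoring text differ.

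The cost is a few extra tables from data already collected. The restricted tables will contain fewer events and be less precise, so they serve as checks on the main table.

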9.2. Subject Exclusion Criteria

Subjects must not meet any of the following exclusion criteria to be eligible for enrollment into the study:

- 1. Any serious medical condition, laboratory abnormality, or psychiatric illness that would prevent the subject from signing the informed consent form
- 2. Active infections requiring systemic antibiotics
- 3. Systemic treatment for B-cell CLL within 28 days of initiation of lenalidomide treatment
- 4. Alemtuzumab therapy within 60 days of initiating lenalidomide treatment
- 5. (removed in protocol amendment #3)
- 6. Prior therapy with lenalidomide
- 7. History of grade 4 rash due to prior thalidomide treatment
- 8. Planned autologous or allogeneic bone marrow transplantation

- 9. Pregnant or lactating females
- 10. Central nervous system (CNS) involvement as documented by spinal fluid cytology or imaging. Subjects who have signs or symptoms suggestive of leukemic meningitis or a history of leukemic meningitis must have a lumbar puncture procedure performed within two weeks prior to initiating study drug
- 11. Prior history of malignancies, other than CLL, unless the subject has been free of the disease for ≥5 years. Exceptions include the following:
 - Basal cell carcinoma of the skin
 - Squamous cell carcinoma of the skin
 - Carcinoma in situ of the cervix
 - Carcinoma in situ of the breast
 - Carcinoma in situ of the bladder
 - Incidental histologic finding of prostate cancer (TNM stage of T1a or T1b)
- 12. History of renal failure requiring dialysis
- 13. Known Human Immunodeficiency Virus (HIV), Hepatitis B Virus (HBV) and/or Hepatitis C Virus (HCV) infection
- 14. Evidence of TLS per the Cairo-Bishop definition of laboratory TLS (subjects may be enrolled upon correction of electrolyte abnormalities)
- 15. Any of the following laboratory abnormalities:
 - Calculated (method of Cockroft-Gault) creatinine clearance of <60 mL/min (creatinine clearance may also be obtained by the 24-hour collection method at the investigator's discretion)
 - Absolute neutrophil count (ANC) $\leq 1,000/\mu L (1.0 \text{ X } 10^9/L)$
 - $-\quad Platelet\ count \leq 50,\!000/\mu L\ (50\ X\ 10^9/L)$
 - Serum aspartate aminotransferase (AST)/serum glutamic-oxaloacetic transaminase (SGOT) or alanine transaminase (ALT)/serum glutamate pyruvate transaminase (SGPT) > 3.0 x upper limit of normal (ULN)
 - Serum total bilirubin > 1.5 x ULN
- 16. Uncontrolled hyperthyroidism or hypothyroidism
- 17. Venous thromboembolism within 12 months

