Neuropathy	Grade 4	Permanently discontinue lenalidomide and follow for PD	
Venous thrombosis/emboli	≥ Grade 3	Hold (interrupt) dose and start anticoagulation;	
sm	4,	 Resume lenalidomide at investigator's discretion (maintain dose level). 	
Hyperthyroidism or hypothyroidism	Any	Interrupt lenalidomide and initiate appropriate medical therapy.	
		 Resume lenalidomide at investigator's discretion (maintain dose level). 	

Table 5: Dose Reduction and Modification Guidelines for Lenalidomide (Continued)

Toxicity	Severity	Action
Serum Creatinine	Grade 2	Interrupt lenalidomide
`	(> 1.5 - 3.0 x ULN)	Evaluate subject weekly (minimum) until the serum creatinine return to baseline
	OR	If serum creatinine resolves to < Grade 1 resume lenalidomide (decrease one dose level)
	Grade 3 (> 3.0 - 6.0 x ULN)	If serum creatinine has stabilized to grade 1 after a minimum of 3 weeks of dose interruption resume lenalidomide at the investigator's discretion (decrease one dose level)
		 If serum creatinine has not stabilized to ≤ grade 1 after 5 weeks of dose interruption:
		 Permanently discontinue lenalidomide and follow for PD at the investigator's discretion OR Contact the Celgene Medical Monitor to discuss subject status
		 If the serum creatinine worsens at any time to > Grade 3, or if dialysis is indicated, permanently discontinue lenalidomide and follow for PD
	pR(Upon resumption of lenalidomide, evaluate subject weekly x 2 weeks to ensure the serum creatinine does not worsen; if the serum creatinine again worsens during those 2 weeks, permanently discontinue and follow for PD
Serum Creatinine	Grade 4 (> 6.0 x	
Sorum Creatinine	ULN) OR	Permanently discontinue lenalidomide and follow for PD
	if dialysis is indicated	

Table 5: Dose Reduction and Modification Guidelines for Lenalidomide (Continued)

Toxicity	Severity	Action
TLS	Laboratory TLS or Grade 1 TLS	Same dose of lenalidomide will be continued without interruption or dose reduction at the investigator's discretion.
		 Hospitalize subjects with Grade 1 TLS, (hospitalization for laboratory TLS will be per investigator's discretion)
		 Provide with vigorous intravenous hydration and rasburicase therapy as needed to reduce hyperuricemia, until correction of electrolyte abnormalities.
		 Dose escalation to the next consecutive dose level is permitted when laboratory TLS is resolved and Grade 1 TLS is resolved to Grade 0.
TLS	≥ Grade 2	Interrupt lenalidomide therapy.

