21. APPENDICES

21.1. Adverse Event

An adverse event (AE) is any noxious, unintended, or untoward medical occurrence occurring at any dose that may appear or worsen in a subject during the course of a study. It may be a new intercurrent illness, a worsening concomitant illness, an injury, or any concomitant impairment of the subject's health, including laboratory test values (as specified by the criteria below), regardless of etiology. Any medical condition that was present prior to the signing of informed consent and that remains unchanged or improved should not be recorded as an AE. If there is a worsening of that medical condition, this should be considered an AE. A diagnosis or syndrome should be recorded on the AE page of the Case Report Form rather than the individual signs or symptoms of the diagnosis or syndrome.

All AEs will be recorded by the Investigator(s) from the signing of informed consent to the treatment discontinuation visit. All AEs that lead to study discontinuation should be followed until resolution or stabilization. For subjects who discontinue study treatment but continue to be followed every 28 days until PD or new CLL therapy, AEs will be reported until 30 days post last dose of study drug or until study discontinuation, whichever occurs last. SAEs will be reported from time informed consent form is signed to 30 days post last dose of study drug. SAEs will be reported at any time post last dose of study drug if it is considered related to study drug. AEs will be recorded on the AE page of the eCRF and in the subject's source documents.

Abnormal laboratory values defined as adverse events

An abnormal laboratory value is considered to be an AE if the laboratory abnormality is characterized by any of the following:

- Results in discontinuation from the study.
- Requires treatment, modification/interruption of study drug dose, or any other therapeutic intervention.
- Is judged by the Investigator(s) to be of significant clinical importance.

If a laboratory abnormality is one component of a diagnosis or syndrome, then only the diagnosis or syndrome should be recorded on the AE page of the eCRF. If the abnormality was not a part of a diagnosis or syndrome, then the laboratory abnormality should be recorded as the AE.

Serious adverse event

A serious adverse event (SAE) is any AE which:

- Results in death

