For each SAE, the Investigator(s) will provide information on severity, start and stop dates, relationship to study drug, action taken regarding study drug, and outcome.

Classification of severity

For both AEs and SAEs, the investigator(s) must assess the severity of the event.

The severity of AEs will be graded based upon the subject's symptoms according to National Cancer Institute (NCI) Common Terminology Criteria (CTCAE, Version 3.0) with the exceptions of hematological toxicities and TLS. Hematological toxicities will be graded as specified in the iwCLL guidelines for the diagnosis and treatment of chronic lymphocytic leukemia (Hallek, 2008) (Appendix 21.4). TLS will be graded as specified by the Cairo-Bishop grading system (Appendix 21.3). AEs will be evaluated for severity according to the following scale:

Grade 1 = Mild

Grade 2 = Moderate

Grade 3 = Severe

Grade 4 = Life Threatening or disabling AE

Grade 5 = Death

Classification of Relationship/Causality of adverse events (SAE/AE) to study drug

The Investigator(s) must determine the relationship between the administration of study drug and the occurrence of an AE/SAE as Not Suspected or Suspected as defined below:

Not suspected: The temporal relationship of the adverse event to study drug

administration makes a causal relationship unlikely or remote, or other medications, therapeutic interventions, or underlying conditions provide a sufficient explanation for the

observed event

Suspected: The temporal relationship of the adverse event to study drug

administration makes a causal relationship possible, and other medications, therapeutic interventions, or underlying conditions do not provide a sufficient explanation for the observed event.

Monitoring and reporting of adverse events

All subjects will be monitored for AEs during the study. Assessments may include monitoring of any or all of the following parameters: the subject's clinical symptoms; laboratory, pathological, radiological, or surgical findings; physical examination findings; or other appropriate tests and procedures.

Immediate reporting of serious adverse events

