21.3. Cairo-Bishop Definition and Grading of Tumor Lysis Syndrome (Cairo, 2004)

Cairo-Bishop Definition of Laboratory Tumor Lysis Syndrome (LTLS)

Uric Acid	\geq 476 µmol/l (\geq 8.0 mg/dl) or 25% increase from baseline	
Potassium	\geq 6.0 mmol/l (\geq 6.0 mEq/l) or 25% increase from baseline	
Phosphorous	\geq 1.45 mmol/l (\geq 4.5 mg/dl) or 25 % increase from baseline	
Calcium	\leq 1.75 mmol/l (\leq 7.0 mg/dl) or 25% decrease from baseline	ON

Laboratory tumor lysis syndrome (LTLS) is defined as either a 25% change or level above or below normal, as defined above, for any two or more serum values of uric acid, potassium, phosphate, and calcium within 3 days before or 7 days after the initiation of chemotherapy. This assessment assumes that a patient has or will receive adequate hydration (\pm alkalinization) and a hypouricaemic agent(s).

Cairo-Bishop Definition of Clinical TLS

The presence of laboratory TLS and one or more of the following criteria:

- 1. Creatinine: ≥ 1.5 ULN (age ≥ 12 years or age adjusted)
- 2. Cardiac arrhythmia / sudden death
- 3. Seizure*

ULN, Upper limit of normal

Cairo-Bishop Grading System for TLS

Grade	LTLS	Creatinine	Cardiac Arrythmia	Seizure
0	-	≤1.5 x ULN	None	None
1	+	1.5 x ULN	Intervention not indicated	None
2	+	> 1.5 – 3.0 x ULN	Non-urgent medical intervention indicated	One brief generalized seizure; seizure(s) well controlled or infrequent; focal motor seizures not interfering with ADL
3	ţC)	> 3.0 – 6.0 x ULN	Symptomatic and incompletely controlled medically or controlled with device	Seizure in which consciousness is altered; poorly controlled seizure disorder; breakthrough generalized seizures despite medical intervention
4	+	> 6.0 x ULN	Life-Threatening	Seizures of any kind that are prolonged, repetitive, or difficult to control
5	+	Death*	Death*	Death*

LTLS, laboratory tumor lysis syndrome; ULN, upper limit of normal; ADL, activities of daily living

^{*}Not directly attributable to a therapeutic agent

^{*}Probably or definitely attributable to clinical TLS

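### Laboratory TLS is summarised only where it was recorded as an adverse event; the planned shift tables cannot identify it from the chemistry

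*SAP*

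**What the plan says.** **Analysis.** SAP 12.1 treats TLS as an adverse event: "The adverse event of Tumor Lysis Syndrome (TLS) will be analyzed according to the grading system as recommended by Cairo-Bishop grading system". The protocol synopsis also names TLS among the clinically important AEs to be summarised. For laboratory values, SAP 12.2 uses NCI CTCAE v3.0 grades: "Shift tables demonstrating the changes from baseline to the worst severity grade observed during the treatment phase will be displayed for each treatment arm". Protocol 15.8 adds cross-tabulations of laboratory abnormalities.

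**Definition.** Protocol Appendix 21.3 defines laboratory TLS as a joint, timed event. It needs a qualifying change in "two or more serum values of uric acid, potassium, phosphate, and calcium within 3 days before or 7 days after the initiation" of treatment. Each analyte qualifies by an absolute level or by a 25% change from baseline.

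**Use in the trial.** Exclusion criterion 14 (Protocol 9.2) is "Evidence of TLS per the Cairo-Bishop definition of laboratory TLS". Table 5 (Protocol 10.2.3) has a row for laboratory or Grade 1 TLS. It lets the same dose continue at the investigator's discretion, says "Provide with vigorous intravenous hydration and rasburicase therapy as needed to reduce hyperuricemia", and adds: "Dose escalation to the next consecutive dose level is permitted when laboratory TLS is resolved".

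**When a laboratory abnormality becomes an AE.** Under Protocol Appendix 21.1 there are three routes. The abnormality leads to discontinuation, or it meets "Requires treatment, modification/interruption of study drug dose, or any other therapeutic intervention", or the investigator judges it clinically important. A component of a syndrome is then recorded as the syndrome.

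**The concern.** The protocol uses one definition of laboratory TLS to decide who enters and who may escalate. It also schedules chemistry on Days 2, 4, 8, 15 and 22 of cycle 1 and of the first cycle at each new dose level. The safety analysis, on its visible text, never applies that definition to the chemistry. Whether an untreated laboratory TLS is counted therefore depends on an investigator noticing it and judging it worth recording, although the values that define it are in the database.

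TLS was the early harm behind the redesign of the earlier study (Protocol 5.3.2.3), where two of the affected patients died. The present trial compares starting doses with safety as its primary objective. A count of laboratory TLS made by the same rule in every subject would be informative about the first weeks at each starting dose.

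**Working it through.** No stated sample size, power or error rate is in question, so there is no plan figure to reproduce. The check is whether the planned outputs determine the number of subjects with laboratory TLS.

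**1. Definition against output.**

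| Element | Appendix 21.3 | SAP 12.2 shift tables |
|---|---|---|
| Analytes | at least 2 of 4 jointly | each parameter separately (my reading of the SAP's reference to relevant parameters; the four are not named) |
| Criterion | absolute level or 25% change | CTCAE grade |
| Time | 3 days before to 7 days after initiation | worst value over the whole treatment phase |

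The joint condition and the window are lost whatever the CTCAE limits are; the documents do not reproduce those limits.

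**2. Separate counts do not fix the joint count.** Suppose each of the four analytes is abnormal in m of n = 35 subjects (m is assumed; the documents give none). The most subjects with two or more abnormal is 4m/2. The fewest is the smallest k with 4k + (35 − k) ≥ 4m, or 0 if 4m ≤ 35.
- m = 4: 0 to 8 subjects (0% to 23%)
- m = 7: 0 to 14 (0% to 40%)
- m = 10: 2 to 20 (6% to 57%)

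**3. The 25% limit can be met below the absolute limit.** The baselines at which the two coincide are:
- potassium 6.0/1.25 = 4.8 mmol/L
- uric acid 8.0/1.25 = 6.4 mg/dL
- phosphorus 4.5/1.25 = 3.6 mg/dL
- calcium 7.0/0.75 = 9.33 mg/dL

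Below the first three values, or above the calcium value, the 25% limit comes first. Example with assumed baselines: potassium 4.0 to 5.0 mmol/L (4.0 × 1.25) and phosphorus 3.0 to 3.75 mg/dL (3.0 × 1.25). Two analytes qualify, although neither reaches 6.0 or 4.5.

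**4. What the AE route catches.** Putting Table 5 beside Appendix 21.1, a case given hydration or rasburicase, a case with a dose change or discontinuation, and a case judged important all qualify as AEs. The remainder is laboratory TLS that was not recognised, or was left untreated at the same dose and judged unimportant.

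**5. Timing of reported TLS in the earlier study.** Protocol 5.3.2.3 gives 4 cases under the original design, all with onset in the first 15 days. The rationale in the protocol's summary of changes gives 5: 4 in the first 15 days and 1 on day 45. Both sources report 2 cases under the amended design, and the rationale dates them to days 7 and 8. Taking Day 1 as first dose, those are 6 and 7 days after it. A 7-day window thus holds at least 2 and at most 6 cases, out of 4 + 2 = 6 or 5 + 2 = 7. No case is dated between Days 16 and 28.

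**6. Precision.** The exact 95% upper limit for zero events is 1 − 0.025^(1/n): 10.0% for n = 35 and 10.3% for n = 34 (SAP section 3 reports 104 enrolled). For scale, 1 of 52 subjects in the amended earlier study had laboratory TLS only (1.9%). At that rate an arm of 35 would expect 35/52 = 0.67 cases, with probability 1 − (51/52)^35 = 49% of at least one. These are reported cases in a study that started at 2.5 mg, so they do not estimate missed cases here.

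**The case against.** The strongest reply is that the plan follows its own endpoint. The primary endpoint is AE-based, TLS is analysed as an AE on the protocol's scale, and shift tables are routine laboratory output that no one presented as a TLS detector. Coverage is also better than SAP 12.1 and 12.2 alone suggest:
- The synopsis plans a TLS summary.
- SAP 12.1 summarises events of interest by cycle, which would include TLS if it is treated as one.
- SAP 14.1 has the DMC reviewing both AEs and laboratory data.
- Investigators must look for laboratory TLS, because visits are scheduled for it and escalation waits on it. The laboratory-only case in the amended earlier study was in fact reported.

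All of this stands, and it narrows the point to a small remainder of cases. It does not remove it: none of these steps applies the Appendix 21.3 rule to every subject's chemistry.

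A reader might also infer a grading defect. The legible Grade 0 and Grade 1 rows of Appendix 21.3 leave no row for laboratory TLS with creatinine below 1.5 x ULN and no arrhythmia or seizure. This is only a minor note. Table 5 already lists laboratory TLS as a category of its own, Appendix 21.1 also prints a general scale ("AEs will be evaluated for severity according to the following scale"), and the grade table is partly damaged in the available text.

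**Conclusion.** The gap is real but small in scope. On the visible text, TLS is summarised only from recorded AEs, and the SAP 12.2 tables cannot identify laboratory TLS as the protocol defines it. The possible loss is confined to cases that were not recognised, or were left untreated and judged unimportant. Its size is unknown; the documents show no missed case.

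Four stronger readings are tempting but unsupported:
- **Bias between arms.** None is shown. The five cycle 1 chemistry draws are the same in every arm, and the blind held until all patients had completed 3 cycles (Protocol 8.1.6).
- **A defective primary endpoint.** It is AE-based, and the derived count would only supplement it.
- **A demonstrated need for the Day 22 draw.** No dated earlier case falls after Day 15 within cycle 1. The timing shows only that a 7-day window may leave out some second-week cases.
- **Interim rules that ignore TLS.** SAP 6.3 and 14.2 are partly blacked out and Protocol Appendix 21.10 is not in the available text, so this cannot be judged.

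The conclusion assumes that the shift tables take each parameter separately. The missing joint rule and window do not depend on the CTCAE limits.

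**What to change.** As an optional, supplementary analysis in SAP 12.2:
- Derive laboratory TLS by program: two or more of uric acid, potassium, phosphate and calcium meeting the Appendix 21.3 absolute or 25%-change limits, with the last pre-dose value as baseline.
- Use actual assessment dates. Count draws up to 7 days after first dose as the Appendix 21.3 row, with no visit-window allowance; SAP 6.5.1 rules out visit windows. A nominal Day 8 draw taken on Day 9 or 10 then falls in the extension.
- Show later cycle 1 draws, and the first cycle at each new dose level, separately as labelled extensions. For new dose levels, state the anchor date and baseline value, and use subjects entering that level as the denominator.
- Tabulate by starting-dose arm beside the investigator-reported TLS events. Include a row for laboratory TLS without clinical TLS and a row restricted to absolute limits.
- List derived cases with no matching AE, and label the table descriptive.

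The cost is one derived variable, one table and one listing. No new data are needed, because all four analytes are in the local panel (Protocol 13.1). The downside is that the 25% rule will flag minor shifts, so the derived count may exceed the investigators' count. The side-by-side layout and the absolute-limit row let a reader tell these apart.
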